Correlation of Audiovisual Features
With Clinical Variables and
Neurocognitive Functions in Bipolar
Disorder, Mania

01.08.2017

Study Protocol

In order to gather sociodemographic and clinical information, all patients were assessed with semi-structured interviews based on the SKIP-TURK. This form includes: identity, sociodemographic personal and family information, age at disease onset, severity, clinical presentation and used treatments.

Thirty-five male and sixteen female patients who were diagnosed as BD type I, manic episode according to DSM-5 in the mental health service of Erenkoy Mental State Hospital and 24 male and 16 female healthy controls matched for age, gender, educational status were included. During hospitalization in every follow up day (0th- 3rd- 7th- 14th- 28th day) and after discharge on the 3rd month, presence of depressive and manic features for patients was evaluated using YMRS and MADRS.

Video recording is done by a presentation guide including seven tasks such as explaining the reason to come to hospital/participate in the activity, describing happy and sad memories, counting up to thirty, explaining two emotion eliciting pictures. To increase the challenge of automatic discrimination, the Control Subjects were recorded with two additional conditions, where they are asked to portray mania and depression conditions.

To provide a benchmark system and insight about the data, we investigated two different approaches. The first is a direct approach to classify video sessions into BD and normal classes, using audio-visual features. The second is an indirect approach, where we use emotion predictions for Pearson correlation analysis and regression of YMRS drop.

Speech Analysis: Acoustic Feature Extraction

Speech utterances are first separated from the video signal and then a standard set of acoustic descriptors are extracted from the audio signal using the open-source openSMILE tool (Eyben et al, 2013). In our preliminary work, we apply functionals over the whole utterance and compare performances of two sets of functionals. The first set of functionals are those used in INTERSPEECH 2010 baseline features. The second is our proposed set of 10 functionals, which we apply on all LLDs and obtain a supra-segmental feature set of $76 \times 10 = 760$ dimensions.

Three affect classifiers are trained, one with the original 4-classes, one for valence (showing the pleasantness of emotion) and one for arousal (reflecting the activity/vitality of the speaker). The arousal and valence labels are obtained by clustering the original 4-classes into corresponding binary labels (e.g. Happy to positive valence and high arousal, Anger to negative valence and high arousal). The predictions of these affect classifiers are then used as mid-level features to classify bipolar disorder.

Video Processing and Visual Features

The faces are detected, cropped and registered using the method proposed by Xiong and De la Torre (2013) with additional procrustes analysis for frontalization as in (Kaya et al., 2015). Along with the faces, we record both the original and the aligned landmark points for subsequent geometric feature extraction. Also, we extract appearance descriptors from registered faces, using a pre-trained Deep Convolutional Neural Network (DCNN) fine-tuned on a face based emotion corpus (Kaya et al, 2017). From DCNN, we extracted 4096 dimensional features from a convolutional layer and 7 dimensional features (outputs for 7 basic emotions) from the last layer.

Neurocognitive Evaluation

Cambridge Neurophysiological Assessment Battery (CANTAB) are administered to both groups) to assess neurocognitive functions. For patients both in the manic phase(in the first week of hospitalization) and in the remission (at 3rd month after beginning of mania treatment), tests are applied. Applied four different tests and their outcome measures are explained below :

Cambridge Gambling Test: Deliberation time, quality of decision making , risk taking, aversion delay

Emotion Recognition Test: Total rate of happiness, sadness, anger,disgust, fear, surprise

Stop Signal Test: Rate of succesful stops, reaction time, delay of stop signal, reaction time for stop signal, total of true stops

Rapid Visual Processing: Outcome measures cover latency (speed of response), probability of false alarms and sensitivity.

Study groups' sociodemographic and clinical features are defined. Bipolar manic phase patients' first YMRS ratings are correlated with first week neurocognitive functions of the same group. The comparison of bipolar mania neurocognitive functions with both bipolar remission and healthy controls are evalauted. The voice analysis results correlation with neurocognitive functions in bipolar mania is examined.

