Correlation of Audiovisual Features
With Clinical Variables and
Neurocognitive Functions in Bipolar
Disorder, Mania

01.08.2017

Statistical Analysis

Speech and Video Analysis

Classification Methods

Feature vectors extracted from audio and video are modelled using Partial Least Squares (PLS) regression and Extreme Learning Machines based classifiers(Kaya et al., 2015; 2017).

Neurocognitive Evaluation

Statistical evaluation is done by using SPSS(Statistical Package for Social Sciences) for Windows 18.0 program. Categoric variables are compared with Chi-square test, qualitative variables are compared with dependent and independent sampling t-test and Mann- Whitney U test. Correlation analysis are done with Pearson and Spearman test. Statistical significance is *= $p<0.05$, **= $p<0.01$, all of tests are two-sided.

Emotion predictions for Pearson correlation analysis and regression of YMRS drop

Regression Model

YMRS score temporal change is calculated as, $t1=0$ th day, $t2=3$ rd day, $t3=7$ th day, $t4=14$ th day, $t5= 28$ th day, $t6=90$ th day and $X1=t2/t1$, $X2=t3/t1$, $X3=t4/t1$, $X4=t5/t1$ and $X5=t6/t1$. These proportions are regressed as stepwise linearly to valence, arousal and singular affect scores of first audio recording values.

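### The SAP lists only unadjusted two-group tests for mania versus controls on CANTAB, so the matching variables (age, gender, education) go unused and some precision may be lost

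*Protocol*

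**What the plan says.** The Study Protocol section gives the patient group as "Thirty-five male and sixteen female patients who were diagnosed as BD type I, manic episode according to DSM-5", and says that "24 male and 16 female healthy controls matched for age, gender, educational status were included". It states no matching ratio or tolerance and gives no summary of age or education in either group.

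The Protocol's Neurocognitive Evaluation section lists outcome measures for four CANTAB tests and sets the aim: "The comparison of bipolar mania neurocognitive functions with both bipolar remission and healthy controls are evalauted".

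The SAP's Neurocognitive Evaluation section says that "qualitative variables are compared with dependent and independent sampling t-test and Mann- Whitney U test", and that "all of tests are two-sided" (reading qualitative there as quantitative). Besides these it names only the chi-square test and Pearson and Spearman correlation. It does not say which test serves which comparison. The only regression of clinical scores in the SAP is for YMRS change: "These proportions are regressed as stepwise linearly to valence, arousal and singular affect scores of first audio recording values". That model is not a CANTAB group comparison.

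**The concern.** By matching on age, gender and education, the investigators treated these variables as relevant to the comparison with controls. The listed tests then set them aside. Two things could follow.

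- **Precision.** Even where matching works well, the variance that these variables explain within groups stays in the error term, and the interval for the mania-control difference is wider than it need be.
- **Residual imbalance.** Where group-level matching is only approximate, any leftover difference passes straight into the contrast.

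The comparison with healthy controls is the only one with an external reference group, and it covers all 4 + 6 + 5 + 3 = 18 listed CANTAB outcomes. The mania-versus-remission comparison is within patients and is not affected.

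**Working it through.** The plan states no sample-size, power or SD figure, so there is nothing to reproduce. The inputs from the documents are the counts in the Study Protocol section and the two-sided 0.05 level in the SAP. The explained variance R², the sex effect and the true difference are assumptions, shown as ranges.

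**1. What the counts show about matching**
- Patients: 35 + 16 = 51, of whom 35/51 = 68.6% are male. Controls: 24 + 16 = 40, of whom 24/40 = 60.0% are male.
- Groups of 51 and 40 cannot all be one-to-one pairs.
- The difference in male share is 8.6 points (95% CI -11.2 to +28.4), a standardised difference of 0.18. Chi-square without correction is 0.73, p = 0.39.
- The unequal split matters little in itself. Efficiency relative to an equal split of 91 is (0.2097/0.2112)² = 0.985, a loss of about 1.5%.

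**2. Precision of the unadjusted contrast**
- SE = SD × √(1/51 + 1/40) = 0.211 SD.
- Difference detectable with 80% power = (1.960 + 0.842) × 0.211 = 0.59 SD.

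**3. Precision after adjustment**

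Adjusted SE = SE × √(1 − R²), where R² is the within-group variance explained by age, sex and education.

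| Assumed R² | Change in SE | Detectable difference | Power at an assumed 0.5 SD |
|---|---|---|---|
| 0 | none | 0.59 SD | 65.8% |
| 0.10 | −5.1% | 0.56 SD | 70.4% |
| 0.20 | −10.6% | 0.53 SD | 75.4% |
| 0.30 | −16.3% | 0.50 SD | 80.8% |

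The table leaves out the cost of fitting the covariates. Three extra terms raise the SE by about √(89/86) − 1 = 1.7%. The observed sex imbalance alone raises it by about 0.4%. The cost at R² = 0 is therefore about 2%. With the 1.7% counted, the reductions at R² = 0.10/0.20/0.30 become about 3.5/9.0/14.9%.

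**4. Bias from the one imbalance that can be checked**

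Shift = 0.0863 × assumed sex effect.
- Sex effect 0.2 SD: 0.017 SD, or 8% of one SE; type I error 5.1%.
- Sex effect 0.3 SD: 0.026 SD, or 12% of one SE; type I error 5.2%.
- Sex effect 0.5 SD: 0.043 SD, or 20% of one SE; type I error 5.5%.

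No such calculation is possible for age or education, because the documents give no figures.

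**The case against.** **The plan claims no more than it delivers.** The Protocol says matched, not paired. Group-level matching with unequal numbers is legitimate, and nothing in the documents offers a balance test as proof of comparability; the p-value above is this review's own. This stands. The point is only that the matching variables go unused in the analysis.

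**Absence of adjustment is inferred.** The SAP does not assign tests to comparisons. That is true, but no listed method adjusts a group difference, and a dependent t-test cannot take 51 patients and 40 controls as pairs.

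**The gain is not assured.** This also stands. The documents give no R², and at R² near 0 adjustment is slightly worse.

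**A stronger reading: inflated false positives.** A reader might infer that imperfect matching makes the unadjusted tests reject too often. Suppose a leftover 0.2 to 0.4 SD gap in age or education, correlated 0.3 to 0.5 with the score. The contrast shifts by 0.06 to 0.20 SD. Adding that shift to the test statistic with its variance unchanged gives rejection rates of about 6 to 16%. The documents do not support this, for two reasons.

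- The gaps are invented: the Protocol says controls were matched on both variables and reports no figures that contradict it.
- The calculation fits only a systematic gap between the populations. For an imbalance realised in the sample, the variance of the estimate falls by the factor 1 − r² while the t-test keeps the full SE. At 0.4 SD and r = 0.5, the shift is 0.20/0.211 = 0.947 and the spread √0.75 = 0.866. Then (1.96 − 0.947)/0.866 = 1.17, which gives about 12.1%. At 0.2 SD and r = 0.3 the rate is 4.9%.

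The range is then about 5 to 12%. With exact balance the unadjusted test is conservative: 3.9/2.8/1.9% at R² = 0.10/0.20/0.30.

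**Conclusion.** The point holds as a conditional loss of precision. No listed method uses age, sex or education in the mania-control contrast, although controls were chosen on them. Before the roughly 2% fitting cost, the SE could fall by about 5/11/16% if the three variables explain 10/20/30% of a score's variance. Those R² values are assumptions, and the gain disappears as R² approaches zero.

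Bias is secondary. The documented sex imbalance is compatible with chance and worth about 0.02 to 0.04 SD for assumed sex effects of 0.2 to 0.5 SD. Imbalance in age or education is unknown rather than shown. Adjustment would remove its linear part if it exists. Confidence is high that no adjusted comparison is named, and moderate about how much that matters.

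**What to change.** In the SAP's Neurocognitive Evaluation section, make the main mania-versus-control analysis a linear model of each CANTAB outcome on group, age, sex and educational status. Educational status should enter as it was recorded for matching, since the documents do not show that years of education are available.

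For each outcome, fix the scale in advance, or specify robust or bootstrap standard errors where skewness is expected, so that no choice of transformation depends on the data across 18 outcomes. A rank-transformed model is a poor main analysis because it gives no interpretable adjusted difference.

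Report the adjusted difference with its 95% CI. Keep the t-test or Mann-Whitney U as a secondary analysis, and state which test belongs to which comparison. Tabulate age, sex and education by group so that a reader can judge the matching.

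The cost is SAP wording and three degrees of freedom out of 91 participants (more if education enters as several categories), or about 2% of the SE if the covariates turn out not to matter. Matching required these variables in both groups, but the Protocol describes the structured interview for patients only, so the sponsor should confirm that controls' values are on file. SPSS, already named, fits the linear model.

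### Speaking instructions appear to differ between patients and controls, and the plan has no analysis that separates the effect of the instruction from the illness in the BD-versus-normal classification

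*Protocol*

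**What the plan says.** The paragraph on video recording in the Protocol, under the heading Study Protocol, states: "Video recording is done by a presentation guide including seven tasks". It then gives examples, one of which is "explaining the reason to come to hospital/participate in the activity". None of the other examples (happy and sad memories, counting, two pictures) carries an alternative wording.

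The same paragraph adds that "the Control Subjects were recorded with two additional conditions, where they are asked to portray mania and depression conditions", and gives the purpose: "To increase the challenge of automatic discrimination". No such condition is described for patients.

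The direct approach is to "classify video sessions into BD and normal classes, using audio-visual features". Under Speech Analysis, the Protocol says of its preliminary work that "we apply functionals over the whole utterance". It also says that the outputs of the valence, arousal and four-class affect classifiers serve as intermediate features for classifying bipolar disorder.

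The SAP, under Classification Methods, names Partial Least Squares regression and Extreme Learning Machines. It does not say which tasks or sessions enter, how acted sessions are labelled, how the data are split, or which performance measure is reported.

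**The concern.** Two features of the recording procedure line up with group membership.

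- **The prompt.** If patients explain why they came to hospital and controls explain why they joined in, the content of the speech probably differs for a reason other than the illness itself. Because predicted emotion feeds the classifier, that difference has a direct route into the result. This is ordinary confounding, and it would tend to make the groups look easier to separate.
- **The acting.** Only controls act. Acted sessions labelled normal are hard negatives and may lower specificity. They may instead raise it, if the classifier learns to recognise acting.

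At stake is what the BD-versus-normal result means. A single figure over all tasks and sessions could not be read as discrimination of the illness. The Protocol offers this work as a benchmark, and a benchmark depends on a defined test set.

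**Working it through.** The documents give no accuracy target, result or sample-size calculation, so there is no stated figure to reproduce. The arithmetic below shows how far the handling of acted sessions could move a pooled result.

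**Inputs from the Protocol**
- Patients: "Thirty-five male and sixteen female patients", so 35 + 16 = 51.
- Controls: "24 male and 16 female healthy controls matched for age, gender, educational status", so 24 + 16 = 40.
- Acted conditions: 2 per control, none for patients.

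**Assumptions not in the documents**
- Each control has one ordinary session, and each acted condition is a separate session labelled normal.
- Each patient has 1 to 6 sessions. The SAP's Regression Model refers to a first audio recording, so more than one may exist; the number is not stated.
- Sensitivity is 0.80 and specificity on ordinary control sessions is 0.85. Specificity on acted sessions is varied.

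**Step 1: make-up of the control sessions.** Acted: 40 × 2 = 80. Total: 40 × 3 = 120. Share acted: 80/120 = 66.7%.

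**Step 2: pooled specificity** = (40 × ordinary + 80 × acted)/120.
- Acted 0.60: (34 + 48)/120 = 68.3%.
- Acted 0.95: (34 + 76)/120 = 91.7%.

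**Step 3: accuracy from always guessing the larger class.**

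| Sessions per patient | Without acted sessions | With acted sessions as normal |
|---|---|---|
| 1 | 51/91 = 56.0% | 120/171 = 70.2% |
| 6 | 306/346 = 88.4% | 306/426 = 71.8% |

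**Step 4: overall accuracy, one session per patient.** Correct calls among patients: 51 × 0.80 = 40.8. Correct calls among ordinary control sessions: 40 × 0.85 = 34.
- Without acted sessions: 74.8/91 = 82.2%.
- Acted specificity 0.50: (74.8 + 40)/171 = 67.1%.
- Acted specificity 0.85: (74.8 + 68)/171 = 83.5%.
- Acted specificity 1.00: (74.8 + 80)/171 = 90.5%.

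Accuracy shifts even when acted and ordinary sessions are equally easy (82.2% to 83.5%), because the class mix has changed.

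**Step 5: the prompt.** One of seven tasks shows alternative wording. Nothing in the documents allows its effect on the features to be estimated.

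**The case against.** The best defence is that the documents are silent here rather than wrong, and much of it stands.

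- A reader might infer that acted sessions are in the normal class. A two-class target and healthy speakers make that likely, but neither document says so. The recordings could be a test-only challenge or be left out.
- A reader might infer that patients and controls certainly receive different prompts. The documents show only a slash and do not assign either wording to a group. The list is introduced as examples, so neither this task's position in the guide nor the sameness of the other six is established.
- The portrayals may be segments within one recording, in which case 80 of 120 does not apply. The sensitivity and specificity values are illustrative.
- The whole-utterance statement describes preliminary work and does not show that tasks are merged.
- Acted sessions are a legitimate, deliberate hard test, with the purpose stated.
- No single pooled figure is announced. The SAP's regression of YMRS change does not depend on the control portrayals.

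These points rule out calling the result inflated or the plan numerically wrong. They do not remove the problem. The prompt most naturally reads as group-specific, acting is confined to controls, emotion predictions feed the classifier, and no planned analysis separates instruction from illness.

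**Conclusion.** The concern holds in conditional form. As written, the plan permits a BD-versus-normal result that mixes the speaking instruction with the illness, and it leaves undefined how a potentially large block of control recordings is used. If acted sessions are pooled as normal under the assumed session counts, two-thirds of control sessions are acted. In the one-session-per-patient illustration, accuracy then lies anywhere from 67.1% to 90.5%, against 82.2% without them. The direction is not determined, and the prompt effect has no size that the documents can supply.

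This is a low-cost improvement to interpretability. The documents do not support the stronger statement that acted sessions are known to make up two-thirds of the normal class.

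**What to change.** In the SAP's Classification Methods section:

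1. State the prompt wording for each group and task. State the label given to acted sessions and whether they enter training, testing or neither.
2. Make the main BD-versus-normal comparison use ordinary sessions and only the tasks confirmed to have the same prompt in both groups. Report the all-task result as a sensitivity analysis.
3. Keep the acted sessions as the intended challenge, but report specificity separately for ordinary, acted-mania and acted-depression sessions.
4. Keep all recordings of one person on the same side of any training/test split. Otherwise a classifier trained on a control's ordinary session may recognise that person in the acted ones and overstate specificity.

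The cost is SAP wording, slightly less data per session in the main comparison, and some extra analysis of existing recordings.

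### Does the mania versus remission CANTAB comparison need changing because remission is given a date but no symptom criterion?

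*Protocol*

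**What the plan says.** The Protocol, under Neurocognitive Evaluation, gives patients two CANTAB sessions. The first is "in the manic phase(in the first week of hospitalization") and the second "in the remission (at 3rd month after beginning of mania treatment"). It then states: "The comparison of bipolar mania neurocognitive functions with both bipolar remission and healthy controls are evalauted". The only planned link between symptom severity and CANTAB concerns the start of the episode: "first YMRS ratings are correlated with first week neurocognitive functions of the same group".

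Symptom ratings at month 3 are part of the schedule. The Protocol's opening section says that "after discharge on the 3rd month, presence of depressive and manic features for patients was evaluated using YMRS and MADRS".

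In the SAP (Regression Model), the day-90 YMRS appears once, as the numerator of the fifth ratio to the day-0 score. Of the five ratios the SAP says: "These proportions are regressed as stepwise linearly to valence, arousal and singular affect scores of first audio recording values". CANTAB is not in that regression. MADRS is named in no analysis. The SAP's sentence on Pearson and Spearman correlations names no variables or time points.

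**The concern.** Remission describes symptoms, and a date alone does not establish it. If everyone who returned at month 3 was tested and called remitted, the paired comparison would estimate the change from week 1 to month 3 but be read as the change in remission. Suppose some patients still had symptoms and had recovered less cognitively. The comparison would then understate the change in remission, and a small or null result could be taken as impairment that persists in remission.

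The plan appears to hold the means to check this and not to use them. YMRS and MADRS are rated at month 3, and severity is treated as relevant to CANTAB at week 1, but there is no month-3 counterpart. The day-90 ratio is no substitute, because it does not give a level. With assumed baselines of 20 and 40, a ratio of 0.30 is a YMRS of 0.30 × 20 = 6 or 0.30 × 40 = 12.

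**Working it through.** **No plan figure to reproduce.** The documents give no sample-size calculation, effect size, month-3 score or remission rate for this comparison. The inputs from the documents are 35 + 16 = 51 patients (Protocol, opening section) and two-sided tests at 0.05 (SAP, Neurocognitive Evaluation). Everything else below is assumed.

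**Reading the label.** The two sessions are described in the same form: a clinical state, then its timing in parentheses.
- Manic phase: first week of hospitalization. The date does not define mania; the Protocol requires a DSM-5 diagnosis.
- Remission: third month of treatment. By the same construction the date says when, and the state is judged otherwise. The judging rule is not written down.

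So there are two readings. If only remitted patients were tested, the label holds and the pairs are a selected part of the 51. If all were tested, the label is looser than the data. The text does not decide between them.

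**Size if all were tested.** Let f be the share unremitted, k the fraction of the remitted patients' change that they show, and 0.40 SD of the change score the assumed change in remission.
- Mean change relative to the change in remission: 1 − f(1 − k)
- Standardized effect: d = 0.40[1 − f(1 − k)] / √(1 + 0.16(1 − k)² f(1 − f))
- Power: paired t-test, noncentral t, n − 1 degrees of freedom, two-sided 5%

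Example, f = 0.2 and k = 0: relative mean 0.80; d = 0.32 / √(1 + 0.16 × 0.16) = 0.316; power at n = 51 is 60.0%.

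| k | f | Relative mean | Power, n = 51 | Power, n = 40 |
|---|---|---|---|---|
| any | 0 | 100% | 80.0% | 69.4% |
| 0 | 10 / 20 / 30% | 90 / 80 / 70% | 70.7 / 60.0 / 48.8% | 59.7 / 49.6 / 39.7% |
| 0.5 | 10 / 20 / 30% | 95 / 90 / 85% | 75.7 / 71.0 / 66.0% | 64.8 / 60.0 / 55.1% |
| 1 | 10 / 20 / 30% | 100 / 100 / 100% | 80.0% | 69.4% |

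The result runs from no effect to a large one, depending wholly on f and k, and the documents give neither.

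**Would a remitted-only analysis help?** The subset would have about 51 × 0.9 = 46, 51 × 0.8 = 41 or 51 × 0.7 = 36 patients. Power at 0.40 is 75.6 / 70.5 / 64.6%.
- Against k = 0.5 it is slightly below the all-patient 75.7 / 71.0 / 66.0%.
- Against k = 0 it is above 70.7 / 60.0 / 48.8%, by 4.9, 10.5 and 15.8 points.

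The gain therefore depends on the more extreme assumption. The subset is also chosen on an outcome measured after baseline.

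**Would correlating CANTAB change with month-3 symptoms help?** The Protocol lists 4 + 6 + 5 + 3 = 18 CANTAB outcomes. Two symptom scales give 18 × 2 = 36 correlations, and 36 × 0.05 = 1.8 nominally significant results would be expected by chance. At n = 51, a Spearman correlation must be about 0.39 for 80% power. In the scenarios above, the correlation of change with unremitted status (a yes/no indicator, Fisher z) is:
- k = 0: 0.12 / 0.16 / 0.18, power 13.2 / 19.7 / 24.4%
- k = 0.5: 0.06 / 0.08 / 0.09, power 7.0 / 8.6 / 9.7%

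A null result would say almost nothing about the label.

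**Timing of the visit.** The month-3 contact is worded three ways: after discharge in the third month, the third month from the start of treatment, and day 90. Taking a month as 30 days, 3 × 30 = 90, and a visit in month 3 can fall after discharge, so the three are compatible. Nothing in the text puts the ratings and the second CANTAB session at different visits.

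**The case for a change.** The strongest case for a change is that it would cost almost nothing. Calling the comparison week 1 versus month 3, and tabulating month-3 YMRS and MADRS for patients with both CANTAB tests, needs no cut-off and no new data, and would serve under either reading. Neither the Protocol's general line on clinical features nor the SAP's general line on correlations commits the study to that table.

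The textual part of this stands: no criterion is written, and no named output shows how symptomatic the retested patients were. But a table of clinical features at each assessed state is routine in a report of this kind. The Protocol says that the study groups' clinical features are described, directly before it sets out the CANTAB comparisons, and the ratings for such a table are already scheduled. In a plan this brief, silence is weak evidence that those levels would go unreported.

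It is also argued that the plan itself treats month-3 symptoms as open, because it rates them and models the day-90 ratio. That carries little weight. Month 3 receives the same ratings as every other visit, and the fifth ratio is built like the other four. It would vary between patients even if all were remitted.

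**Conclusion.** The concern is accurate on the text but does not call for a change to the plan. It amounts to an unwritten definition and a descriptive table that sensible analysts would supply: how remission was judged, how many patients have both CANTAB tests, and their month-3 YMRS and MADRS levels. The choice of criterion is a clinical matter for the sponsor.

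The paired test and its error rate are untouched. Only interpretation is at stake, and only if all patients were tested, some were still symptomatic, and those patients improved less. The documents establish none of the three. Under the assumed values the all-patient mean is 70 to 100% of the change in remission, and power at 51 pairs is 48.8 to 80.0% for an assumed 0.40 SD change; these figures are illustrative. The heavier additions bring little: the correlations have 7 to 24% power in the scenarios with dilution, and the remitted subset gains power only if unremitted patients changed hardly at all. Both are exploratory options on which statisticians could reasonably differ.

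### Does correlating first-week CANTAB scores with the first YMRS rating, rather than the rating nearest to testing, undermine the analysis?

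*Protocol*

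**What the plan says.** Three places bear on this.

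- **Protocol, Neurocognitive Evaluation.** CANTAB is given twice to patients: "For patients both in the manic phase(in the first week of hospitalization"), and again at month 3. No day within that first week is fixed. The final paragraph states the analysis: "first YMRS ratings are correlated with first week neurocognitive functions of the same group".
- **Protocol, Study Protocol (visit schedule).** YMRS is rated repeatedly: "During hospitalization in every follow up day (0th- 3rd- 7th- 14th- 28th day) and after discharge on the 3rd month". Three ratings (days 0, 3 and 7) therefore fall in or at the edge of the testing week.
- **SAP.** Under Neurocognitive Evaluation, "Correlation analysis are done with Pearson and Spearman test". Under Regression Model, the ratings are labelled by day: "YMRS score temporal change is calculated as, $t1=0$ th day, $t2=3$ rd day, $t3=7$ th day", and the day-3 and day-7 scores are each divided by the day-0 score.

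That the first rating is the day-0 rating is an inference from the schedule and the SAP's labelling, but a safe one. Neither document matches a CANTAB session to a rating by date, adjusts for test day, or discusses which severity is meant.

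**The concern.** The predictor is measured on day 0 and the outcome possibly some days later, during a week in which the SAP itself models YMRS change. If cognition follows severity at the moment of testing, the day-0 score is an imperfect stand-in for the score that matters. The observed correlation is then the true one multiplied by the correlation between the two YMRS scores. A weak result could reflect timing rather than absence of a relation.

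Ratings on days 3 and 7 are already planned, so pairing each session with the nearest rating looks like an improvement at almost no cost. At stake would be power across 18 named CANTAB outcomes (4 + 6 + 5 + 3) in 51 patients (35 + 16).

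**Working it through.** The documents give no target correlation, SD, power or sample-size calculation, so there is no figure of the plan's own to reproduce. The check has four steps.

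**1. Is the stated analysis complete and consistent?** The sentence in the Protocol names the predictor (first YMRS), the outcome (first-week CANTAB) and the group (patients in mania); the SAP names the method. Nothing elsewhere contradicts it. The SAP's ratios over time belong to a different analysis, the regression on affect scores from the first audio recording.

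**2. How far apart can rating and test be?** Reading the first week as days 0 to 7:

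| Test day | 0 | 1 | 2 | 3 | 4 | 5 | 6 | 7 | Mean |
|---|---|---|---|---|---|---|---|---|---|
| Days from day 0 | 0 | 1 | 2 | 3 | 4 | 5 | 6 | 7 | 28/8 = 3.5 |
| Days from nearest of 0, 3, 7 | 0 | 1 | 1 | 0 | 1 | 2 | 1 | 0 | 6/8 = 0.75 |

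The possible gap is real. Whether it matters depends on the actual test days, on how differently patients improve, and on which severity drives cognition. The documents give none of these.

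**3. What would the alternative gain or lose?** Every input here except n = 51 and the two-sided 0.05 level is assumed. YMRS on day d is Y0 + S·d, with Y0 and S independent, SD(Y0) = 6, mean S = −6/7, SD(S) = (SD of the day-7 fall)/7, and test days equally likely and unrelated to severity. The true correlation is 0.40 with whichever YMRS matters. Power ≈ Φ(atanh(r)·√(n−3) − 1.96), with √(n−4) when test day is adjusted for. A tie on day 5 goes to the earlier rating.

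Worked case, days 0 to 7, fall SD 5.1:

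- E(d²) = 140/8 = 17.5 and Var(d) = 17.5 − 3.5² = 5.25.
- Var(test-day YMRS) = 36 + 17.5·(5.1/7)² + 5.25·(6/7)² = 36 + 9.29 + 3.86 = 49.15.
- Correlation of day-0 with test-day YMRS = 6/√49.15 = 0.856.
- Day-0 pairing: r = 0.40 × 0.856 = 0.342; 0.357 × 6.93 − 1.96 = 0.51; power 70%.
- Nearest rating, adjusted: r = 0.381; 0.401 × 6.86 − 1.96 = 0.79; power 79%.

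Power across the scenarios:

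| Cognition follows | Test days | SD of fall | Day 0 | Nearest, adjusted |
|---|---|---|---|---|
| Test-day YMRS | all day 0 | any | 84% | 84% |
| Test-day YMRS | 0–3 | 5.1 | 80% | 81% |
| Test-day YMRS | 0–7 | 0 | 79% | 78% |
| Test-day YMRS | 0–7 | 2.5 | 77% | 78% |
| Test-day YMRS | 0–6 | 5.1 | 73% | 79% |
| Test-day YMRS | 0–7 | 5.1 | 70% | 79% |
| Test-day YMRS | all day 7 | 5.1 | 59% | 84% |
| Admission YMRS | 0–7 | 5.1 | 84% | 72% |

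Where all patients share one test day, no adjustment is made. In four of the seven test-day scenarios the pairings differ by at most 1 point as rounded. The one large gain needs every patient tested on day 7. If admission severity is what matters, the alternative loses 84 − 72 = 12 points.

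**4. Would reporting both correlations settle which case holds?** Studies of 51 patients were simulated under the days 0–7, SD 5.1 model, taking the adjusted nearest-rating correlation minus the day-0 correlation:

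| Cognition follows | Mean difference | SD | Wrong sign | Same significance verdict |
|---|---|---|---|---|
| Test-day YMRS | +0.039 | about 0.066 | about 28% | about 85% |
| Admission YMRS | −0.044 | about 0.066 | about 25% | about 85% |

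The mean shift is about 0.6 SD (0.039/0.066) or 0.7 SD (0.044/0.066). For one outcome, the comparison is weak evidence about timing.

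**The case for a change.** The strongest argument is that the loss is not bounded by the scenarios above. If day-0 and test-day YMRS correlate at only 0.7, or 0.5, a true correlation of 0.40 shrinks to 0.28, or 0.20, and power falls from 84% to 51%, or 29%. The extra analysis needs no new assessment, leaves the stated one in place, and could be labelled as sensitivity. It would cost one degree of freedom: the correlation detectable with 80% power moves only from 0.384 to 0.387. There is also a route that the scenarios leave out: if sicker patients were tested later, test day could distort even the day-0 correlation.

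The facts behind this stand. The test day is open, no pairing rule is given, and the plan does not say in words whether admission severity or severity near testing is of interest. A sentence on that, and the rating-to-test interval if dates exist, would help a reader.

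It does not follow that the plan is wrong. The low correlations between ratings, and a link between severity and test day, are suppositions that the documents do not support. The alternative has its own weaknesses. Without adjustment, it picks up a pure test-day effect: with an assumed correlation of 0.30 between test day and cognition and no severity effect, its correlation is about 0.08 in size and it is significant in 9% of studies instead of 5%. With adjustment, it gives up some real severity signal (83% to 78% power when all patients improve equally over days 0 to 7). It adds 18 correlations, of which 18 × 0.05 = 0.9 would fall below 0.05 by chance if none were real. It also needs CANTAB dates, which the documents do not say were recorded.

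**Conclusion.** The concern does not hold. The plan states a coherent correlation between admission severity and cognition in the first week, and nothing in the Protocol or SAP makes severity on the test day the target. Calling the day-0 pairing a mismatch requires a different question to be put in its place.

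On the assumed inputs, the alternative gains about 9 points of power in one case (70% to 79%, evenly spread testing, cognition following test-day severity) and loses about 12 in the other (84% to 72%, cognition following admission severity). It makes almost no difference in several more. Setting both correlations side by side would not reliably tell these cases apart. These sizes rest on the assumed correlation of 0.40, the YMRS spread and fall, and the test-day distribution; the actual effect cannot be computed from the documents and may be nil. The choice between the two pairings is one of emphasis, and the stated choice is defensible as it stands.
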